## 2. SYNOPSIS

Title of Study:	Prospective multi-center study comparing REGENETEN in lieu of standard arthroscopic repair of high-grade (>50%) partial-thickness tears
Study Design:	Non-blinded, multi-center
Study Type:	Prospective cohort study
Study Product:	REGENETEN™ Implant
Comparison Group:	Arthroscopic repair of the high-grade (>50%) partial-thickness tear using standard surgical techniques.
Study Purpose:	Demonstrate that REGENETEN is superior to standard repair techniques when surgically treating high-grade (>50%) partial-thickness tears because REGENETEN preserves more of the native tendon footprint resulting in less post-operative pain and faster recovery.
Primary Objective:	To determine if arthroscopic surgical treatment of high-grade (>50%) partial-thickness rotator cuff tears using REGENETEN yields statistically superior participant-rated shoulder function and reduced pain and disability at 3 months following index surgery compared to standard surgical repair techniques.
Secondary Objective:	To generate performance and health economic evidence supporting the use of REGENETEN in treating high-grade (>50%) partial-thickness rotator cuff tears.
Statistical Rationale:	Superiority hypothesis for American Shoulder and Elbow Surgeons (ASES) score at 3 months following index surgery using a minimal clinically important difference (MCID) of 11.1  and a drop-out rate of 15%.
Sample Size:	118 participants (59 per group)
Number of Study Sites:	Up to 12 clinical sites
Targeted Global Regions:	United States
Inclusion Criteria:	Patients will be considered qualified for enrollment if they meet the following criteria:

This document contains information that is confidential and proprietary to Smith & Nephew PLC and Smith & Nephew, Inc. and is intended for use only by Smith & Nephew and its manufacturer. It shall not be reproduced or copied in whole or in part, nor shall the contents be disclosed by any means without prior written permission from Smith & Nephew, nor shall anyone make any use of it that is contrary to the expressed or implied wishes of Smith & Nephew.

Study Protocol—Device	9	>5 smith&nephew		
Prospective multi-center study comparing REGENETEN in lieu of standard arthroscopic repair of high-grade (>50%) partial-thickness tears		Number:           REGEN.PUB.2018.09           Version: 3.0, 10SEP2019           Page: Page 5 of 105		
Exclusion Criteria:	
 
Male or female ≥18 years
 
High-grade (>50% tendon thickness) p
 
Failed conservative medical managerras:         
 
a. Four (4) to six (6) weeks of form home exercises
 
b. Activity modification
 
c. Shoulder injection at the discretion
 
 
 
Able to comply with the post-operative schedule
 
Able to speak and read English
 
Provide written informed consent
 
Any one (1) of the following criteria will disparticipation in the study:
 
Prior shoulder surgery on index should enrollment
 
Failed primary rotator cuff surgery of ti
 
Systemic steroid use (oral, IV) or local within 1 month of enrollment
 
Metastatic disease
 
Concomitant surgeries for bone defect (Latarjet procedures) or for superior la posterior (SLAP)
 
Concomitant biceps tenodesis
 
Rheumatoid arthritis
 
Advanced osteoarthritis
 
Fatty infiltration of the index shoulder 10. Chronic pain disorders (i.e., fibromyals 11. History of insulin dependent diabetes 12. History of heavy smoking (> 1 pack per enrollment
 
Currently involved in any injury litigation claims
 
Hypersensitivity to bovine-derived mating 15. Medical or physical condition that, in the would preclude safe participation in the would preclude safe par

	nent of the tendon tear defined al physical therapy or guided of the surgeon physiotherapy and follow-up squalify a patient from der within 12 months of he index shoulder lly injected at the surgical site ts requiring bone implantation abral tear from anterior to rotator cuff muscle ≥ Grade 3 gia) er day) within 6 months of on or workers compensation terials he opinion of the Investigator,		
Study Duration:	18 months enrollment (estimated), 24 mol endpoint assessed at 3 month follow-up)			
Primary endpoint:	ASES (American Shoulder and Elbow Sur following index surgery	rgeons) score at 3 months		

CONFIDENTIAL AND PROPRIETARY This document contains information that is confidential and proprietary to Smith & Nephew PLC and Smith & Nephew, Inc. and is intended for use only by Smith & Nephew and its manufacturer. It shall not be reproduced or copied in whole or in part, nor shall the contents be disclosed by any means without prior written permission from Smith & Nephew, nor shall anyone make any use of it that is contrary to the expressed or implied wishes of Smith & Nephew.

Prospective multi-center study comparing REGENETEN in lieu of standard arthroscopic repair of high-grade (>50%) partial-thickness tears	Number: REGEN.PUB.2018.09	
	Version: 3.0, 10SEP2019 Page: Page 6 of 105	

Secondary endpoint(s):	
 
Performance endpoints include: 
 
ASES score over initial 3 months following index surgery
 
Single Assessment Numeric Value (SANE) score over initial 3 months following index surgery
 
ASES Visual Analog Scale (VAS) pain score over initial 3 months following index surgery
 
ASES score at 6, 12, 18 and 24 months following index surgery
 
SANE score at 6, 12, 18 and 24 months following index surgery
 
ASES VAS pain score at 6, 12, 18 and 24 months following index surgery
 
Constant-Murley score at 3, 6, 12 and 24 months following index surgery
 
Constant-Murley score at 3, 6, 12 and 24 months following index surgery
 
Cumulative opioid use to treat the index shoulder over 3 months following index surgery
 
Cumulative opioid prescription medication use to treat the index should over 3 months following index surgery
 
Cumulative opioid prescription medication use to treat the index should over 3 months following index surgery
 
Cumulative opioid prescription medication use to treat the index shoulder over 12 months following index surgery
 
Cumulative non-opioid prescription medication use to treat the index shoulder over 12 months following index surgery
 
Duration of shoulder immobilization following index surgery
 
Duration of shoulder immobilization following index surgery
 
Time to return to work by work type (sedentary; laborer)
 
Time to return to sports
 
Incidence of progression to full-thickness tear within 12 months following index surgery
 
MRI assessment of percent filling at 12 months following index surgery
 
Rotator cuff tendon thickness at 12 months following index surgery
 
Rotator cuff tendon thickness at 24 months following index surgery
 
Goutallier classification of rotator cuff at 12 months following index surgery
 
Goutallier classification of rotator cuff at 24 months following index surgery
 
 
 

------------------------	--

This document contains information that is confidential and proprietary to Smith & Nephew PLC and Smith & Nephew, Inc. and is intended for use only by Smith & Nephew and its manufacturer. It shall not be reproduced or copied in whole or in part, nor shall the contents be disclosed by any means without prior written permission from Smith & Nephew, nor shall anyone make any use of it that is contrary to the expressed or implied wishes of Smith & Nephew.

Study Protocol—Device	e	>'smith&nephew	
Prospective multi-center study comparing REGENETEN in lieu of standard arthroscopic repair of high-grade (>50%) partial-thickness tears		Number: REGEN.PUB.2018.09 Version: 3.0, 10SEP2019 Page: Page 7 of 105	
	
 
Sugaya score of rotator cuff at 24 surgery
 
Incidence of revision surgery withi surgery (index shoulder; all causes
 
Economic endpoints include: 
 
Aggregate health care utilization c index surgery
 
Operating room time (index surger
 
Number of steroid injections over surgery
 
Number of unscheduled clinic visit index surgery
 
Number of for-cause imaging proc following index surgery
 
 
 
	n 24 months following index s) osts over 12 months following ry) 12 months following index as over 12 months following redures over 12 months	
Safety Data	
 
Number of physiotherapy sessions index surgery
 
All Adverse Events over 24 months
 
	sover 12 months following	

CONFIDENTIAL AND PROPRIETARY This document contains information that is confidential and proprietary to Smith & Nephew PLC and Smith & Nephew, Inc. and is intended for use only by Smith & Nephew and its manufacturer. It shall not be reproduced or copied in whole or in part, nor shall the contents be disclosed by any means without prior written permission from Smith & Nephew, nor shall anyone make any use of it that is contrary to the expressed or implied wishes of Smith & Nephew.

Study Protocol—Device	Smith&nephew	
Prospective multi-center study comparing REGENETEN In	Number: REGEN.PUB.2018.09	
lieu of standard arthroscopic repair of high-grade (>50%)	Version: 3.0, 10SEP2019	
partial-thickness tears	Page: Page 8 of 105	

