## **STUDY SCHEMATIC**

Schedule of Events	Pre-Op (days -60 to -1)	Surgery (day 0)	3 Mo (±30 days)	6 Mo (±30 days)	12 Mo (±30 days)	18 Mo (±60 days)	24 Mo (±60 days)
Informed Consent	
 
✓
 
						
Inclusion/Exclusion	✓						
Demographics/ Medical History	✓						
Operative Data		~					
ASES Score	~		√t	~	~	~	~
SANE	~		√t	~	~	~	~
Constant-Murley Score	~		~	~	~		$\checkmark$
Participant Diary			√‡	✓‡	✓‡		
Adverse Events		~	~	~	~	~	~
Heath Care Utilization			~	~	~		
Revision Surgery			~	✓	~	~	~
Upper Extremity MRI	√*				~		~

Pre-Op indicates pre-operative; Mo, month(s); SANE, Single Assessment Numeric Evaluation; ASES, American Shoulder and Elbow Surgeons Score including VAS Pain

†The ASES score and SANE will be completed every week (i.e., every 7±3 days) though 3 month follow-up. ‡Participant diaries will be used to document opioid and non-opioid prescription medication use, use of a sling, other related healthcare utilization (i.e. steroid injections, clinic visits, imaging, physiotherapy sessions, etc.) and return to work, driving, and sports. Participant diary will be updated weekly (7±3 days) through 3 month follow-up and monthly (30±7 days) thereafter until 12 months post-surgery.

\*The pre-op MRI is the participant's standard of care MRI and will not follow the study MRI Image Acquisition Protocol which is used for the 12 and 24 month MRIs. The pre-op MRI must occur within 6 months of enrollment into this study. All MRIs will be submitted to the imaging vendor per the Image Transfer Protocol.

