## 9.1.3 Index Surgery (Day 0)

- 1. Confirm eligibility based on arthroscopic visualization of the tear.
- 2. Complete surgical procedure.
- 3. Record operative details as specified in Case Report Forms (CRFs)
- If any adverse events, adverse device effects, or device deficiencies are observed or reported, they must be recorded as instructed in Section 12 – Adverse Events and Device Deficiencies.
- 5. Instruct the participant on proper post-operative care/procedures, including any contraindicated treatments/medication(s).
- 6. Instruct the participant on follow-up procedures, including completing the weekly ASES and SANE questionnaires, completing the weekly diary, and returning for clinical follow-up at 3 months.
- 7. Provide participants with the cohort-specific Physiotherapy Guidelines.

This document contains information that is confidential and proprietary to Smith & Nephew PLC and Smith & Nephew, Inc. and is intended for use only by Smith & Nephew and its manufacturer. It shall not be reproduced or copied in whole or in part, nor shall the contents be disclosed by any means without prior written permission from Smith & Nephew, nor shall anyone make any use of it that is contrary to the expressed or implied wishes of Smith & Nephew.

Study Protocol—Device	Standard Sta
Prospective multi-center study comparing REGENETEN in lieu of standard arthroscopic repair of high-grade (>50%) partial-thickness tears	Number: REGEN.PUB.2018.09
	Version: 3.0, 10SEP2019 Page: Page 29 of 105

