## 9.1.4 Weekly Diary (week 1 to week 12 (±3 days))

- 1. Participant will complete the ASES questionnaire and SANE questionnaire.
- 2. Participant will document opioid and non-opioid prescription medication use, use of sling, other healthcare utilization related to the index shoulder (i.e. steroid injections, clinic visits, imaging, physiotherapy sessions, etc.) and return to work, driving, and sports in their diary.
- 3. Study personnel will remind each study participant to complete the questionnaires and diary weekly via telephone, email, or text.
- 4. Study personnel will remind participant of the importance of complying with the specified Physiotherapy Guidelines.

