## 9.1.5 3 Month Visit (±30 days), 6 Month Visit (±30 days), 12 Month Visit (±30 days), 18 Month Visit (±60 days), and 24 Month Visit (±60 days)

- 1. Complete the ASES questionnaire (all visits), SANE questionnaire (all visits), and Constant-Murley assessment (3, 6, 12 and 24 month visits only).
- 2. Review diary entries for completeness with participant.
- 3. Document any health care utilization involving the index shoulder not recorded in the participant diary (3, 6, and 12 month visits).
- 4. Document any revision surgeries involving the index shoulder (all visits).
- If any adverse events, adverse device effects, or device deficiencies are observed or reported, they must be recorded as instructed in Section 12 – Adverse Events and Device Deficiencies (all visits).
- 6. MRI of index shoulder (12 month and 24 month visits).
- Instruct the participant on follow-up procedures, including returning for the next clinical follow-up (except for the 24 month exit visit).

This document contains information that is confidential and proprietary to Smith & Nephew PLC and Smith & Nephew, Inc. and is intended for use only by Smith & Nephew and its manufacturer. It shall not be reproduced or copied in whole or in part, nor shall the contents be disclosed by any means without prior written permission from Smith & Nephew, nor shall anyone make any use of it that is contrary to the expressed or implied wishes of Smith & Nephew.

Study Protocol—Device	Smith&nephew
lieu of standard arthroscopic repair of high-grade (>50%)	REGEN.PUB.2018.09
	Version: 3.0, 10SEP2019 Page: Page 30 of 105

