## 12.3 REPORTING PROCEDURES

AE of any kind and DD will be recorded in the applicable CRF and source notes. The Investigator will evaluate all AE for relationship to the device and procedure, if applicable, seriousness, and severity. The following timescales should be followed for the AE/DD information to be submitted/entered into the CRF and reported to the Sponsor via the REDCap Cloud EDC system (see Figures 3 and 4):

- ADE and DD without unreasonable delay
- SAE, SADE and DD with potential to cause SADE immediately (i.e. within 24 hours of the Investigator being informed about the event)

For ADE and DD, details of the product/procedure related to the event will be included and where applicable, pictures taken of the device. The deficient product should be retained for return to unless it is contaminated (e.g., used dressings must not be retained). Updates to submitted information will be recorded in the CRF according to the timescales above.

All adverse events will be reviewed by a medically qualified person appointed by the Sponsor to determine which, if any, meet criteria for expedited reporting to the regulatory authorities.

The investigator will inform the IRB of adverse events according to the IRB requirements.

[figure not shown]
This document contains information that is confidential and proprietary to Smith & Nephew PLC and Smith & Nephew, Inc. and is intended for use only by Smith & Nephew and its manufacturer. It shall not be reproduced or copied in whole or in part, nor shall the contents be disclosed by any means without prior written permission from Smith & Nephew, nor shall anyone make any use of it that is contrary to the expressed or implied wishes of Smith & Nephew.

[figure not shown]
Study Protocol—Device	% smith&nephew
lieu of standard arthroscopic repair of high-grade (>50%)	Number: REGEN.PUB.2018.09
	Version: 3.0, 10SEP2019 Page: Page 52 of 105

Depending on the nature of the adverse event, S&N may request copies of the participant's medical records, imaging, operative notes, as well as results of any relevant laboratory tests performed or other documentation related to the AE. If the participant was hospitalized, a copy of the discharge summary may be requested by S&N and should be forwarded as soon as it becomes available. In certain cases, S&N also may request a letter from the Investigator that summarizes the events related to the case.

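### No adverse-event enquiry is scheduled between surgery and the 3-month visit, although participants are contacted weekly, so early events that nobody volunteers may be recorded late, on recall or not at all

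*Combined protocol and SAP*

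**What the plan says.** The Synopsis gives the scope of the safety data as "All Adverse Events over 24 months". Section 12.1.1 defines an AE broadly, so that any untoward medical event counts whether or not the product caused it.

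The AE row of the study schematic and of Table 1 is ticked at surgery and then at 3, 6, 12, 18 and 24 months. The discharge step in Section 9.1.3 tells participants about the weekly questionnaires, the weekly diary and "returning for clinical follow-up at 3 months". It does not mention reporting AEs in between.

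Section 9.1.4 covers weeks 1 to 12. Its first item is "Participant will complete the ASES questionnaire and SANE questionnaire". Its second is the diary, which the schematic footnote describes thus: "Participant diaries will be used to document opioid and non-opioid prescription medication use, use of a sling, other related healthcare utilization", plus return to work, driving and sports. Section 9.1.4 limits the health-care entries to the index shoulder. Its third item is "Study personnel will remind each study participant to complete the questionnaires and diary weekly via telephone, email, or text", and its fourth is a physiotherapy reminder.

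At the visits, Section 9.1.5 has staff check the diary for completeness and says: "If any adverse events, adverse device effects, or device deficiencies are observed or reported, they must be recorded as instructed in Section 12". Section 12.3 requires AEs of every kind to be recorded, and serious events to be reported "within 24 hours of the Investigator being informed about the event".

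**The concern.** The promise covers all AEs, but the plan has no step that asks about them between the day of surgery and the 3-month visit. Sections 9.1.3 and 9.1.5 each carry an AE instruction. Section 9.1.4, which lies between them and describes the most frequent contact in the study, carries none.

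An event in week 2 that has settled by week 6 reaches the database before 3 months only if the participant raises it or the site happens to learn of it. Otherwise it depends on recall at the visit. Section 10.5 summarises AE frequencies by treatment cohort, and those percentages would understate the early period by an unknown amount. Section 10.6 also allows findings from the 3-month data extract to be presented. It does not say whether AE data would be among them, but any early safety summary would rest on this first interval.

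**Working it through.** The plan states no figure for AE capture, so there is nothing to reproduce. The check compares the schedule with the content of the contacts.

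**Inputs.** AE ticks at day 0 and at 3, 6, 12, 18 and 24 months, and visit windows (schematic, Table 1, Section 9.1.5). Weekly contacts for weeks 1 to 12, at 7±3 days (Section 9.1.4 and schematic footnote). Monthly diary at 30±7 days until 12 months (schematic footnote). 118 participants (Section 8.1).

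**1. Time from surgery to the first scheduled AE assessment.** Taking a month as 365.25/12 = 30.44 days:
- nominal: 3 × 30.44 = 91 days
- earliest: 91 − 30 = day 61
- latest: 91 + 30 = day 121

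**2. Contacts already planned in that interval.** 12 per participant, or 118 × 12 = 1,416 in all. This measures opportunity, not events missed.

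**3. Which contacts carry an AE step.**
- Surgery (9.1.3): yes.
- Weekly contacts, weeks 1 to 12 (9.1.4): no. They cover ASES, SANE, medication, sling, index-shoulder care, return to activities and reminders.
- Visits from 3 months (9.1.5): yes, conditional on an event being observed or reported.

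**4. Whether another section fills the gap.** Section 12.3 sets out recording and reporting once an event is known, and its 24-hour limit runs from when the Investigator learns of it. A diary entry for a shoulder-related clinic visit or scan is an indirect signal, but no rule turns it into an AE enquiry. Review of the diary with the participant is first listed at the 3-month visit. An event outside the shoulder, or one that led to no care, has no evident diary field.

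**5. Interval if the weekly contact carried an AE question.** 7 + 3 = 10 days at most between contacts. If the ±3 days is read as a window around each nominal week, the limit is 7 + 3 + 3 = 13 days. If weekly contact stops at week 12 (12 × 7 = day 84), a visit on day 121 leaves 121 − 84 = 37 days. The schematic footnote, which runs weekly completion through the 3-month follow-up, would avoid this. Monthly entries give 30 + 7 = 37 days.

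**6. Later intervals.** Nominal gaps between visits are 183 − 91 = 92, 365 − 183 = 182, 548 − 365 = 183 and 730 − 548 = 182 days. The first interval is therefore not the longest. It stands out because weekly contact already exists within it and is not used. Monthly diary contact offers the same opening up to 12 months.

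**The case against.** The plan is not silent between visits. Section 12.3 is not tied to visits, and the investigator obligations in Section 21.2 require every AE to be recorded. Serious events have a 24-hour rule, and a clock that starts when the Investigator is informed is not a defect in itself. The weekly diary logs shoulder-related visits, imaging, injections and medication, and the weekly ASES includes pain. At 3 months staff add shoulder-related care that the diary missed. This stands, and it narrows the point: what is left is mainly non-serious or non-shoulder events that nobody volunteers. A reader might infer that early harms in general are found late. The documents do not support that.

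A reader might also infer that detection depends on how often each cohort is seen, and so favours REGENETEN. Aftercare is cohort-specific (Section 9.1.6), and objectives #30 and #32 hypothesise fewer unscheduled visits and physiotherapy sessions. The documents do not support this either. Scheduled visits, questionnaires, diary and reminders are identical in both cohorts. Objective #30 concerns unscheduled shoulder visits, defined in Section 9.2.2 as return visits for examination or evaluation, and such visits may themselves result from harm. No section gives physiotherapists a role in detecting AEs, and the physiotherapy guidelines are a separate document. No capture rate is given for either cohort, and equal capture would leave the comparison undistorted.

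The consequence is also limited. This is a post-market study of a cleared device, AEs are not a primary or secondary endpoint, and Section 10.5 is descriptive. The documents do not show that early weeks carry most of the risk; device risks are deferred to the Instructions for Use.

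Finally, a change in AE capture during the study could fall unevenly on the cohorts, because allocation is not randomized and the faster-enrolling cohort closes first (Section 8.2). That stands and shapes the remedy.

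**Conclusion.** The point holds in a limited form. The protocol promises all AEs over 24 months, yet schedules no AE enquiry from surgery until the 3-month visit, nominally day 91 and about day 61 to 121 within the window. Twelve weekly contacts fall in that period and none has an AE item. Unvolunteered early events, mainly non-serious or non-shoulder, may be recorded late, on recall, or not at all.

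The length of the gap follows from the schedule, with a month taken as 30.44 days. The number of events lost cannot be estimated from the documents. Differential detection between cohorts remains a possibility and is not part of the conclusion. The primary analysis, sample size and power are unaffected. This is an inexpensive improvement that should be made, not a flaw that undermines the study's main comparison.

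**What to change.** - Add one fixed AE question to the weekly diary and contact in Section 9.1.4 and to the monthly diary up to 12 months, for example whether there has been any new medical problem or treatment since the last entry. Word it identically in both cohorts and introduce it in both at the same time.
- State that a positive answer, or a diary entry for an unscheduled shoulder-related visit or imaging, triggers AE review under Section 12 when it is received.
- Tick AEs for these contacts in the schematic and Table 1.
- In Section 10.5 and the SAP, summarise AEs by cohort separately for participants treated before and after the change.

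**Cost.** One diary item, edits to a few sections and an IRB-approved amendment, using contacts already planned. Section 15 reserves amendments for exceptional cases, but there is precedent. Version 2.0 added a weekly participant item through week 12 and judged the effect on data collection minimal, with one participant enrolled at the time. Version 3.0 added the Constant-Murley score after 27 participants had been treated.

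**Downside.** Sites need time to follow up positive answers, and more non-serious AEs will be recorded. Capture before and after the change will not be comparable. The split summary discloses that difference but does not remove it, and nothing is recovered for participants already past 3 months.
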